10.1. Details of Study Assessments

Timing of all study assessments is detailed in the Schedule of Study Assessments in **Table 2**.

10.1.1. Informed Consent

At Screening, each subject must provide informed consent in writing after having had adequate time to ask questions and consider his/her participation in both parts of this study. Consent must be obtained prior to any protocol related procedure or assessment that is not part of the subject's normal care. Participating centers will be responsible for assuring that written informed consent is provided by each subject using an informed consent form (ICF) approved by the Institutional Review Board (IRB) or Independent Ethics Committee (IEC) granting approval for the conduct of the study. Documentation of IRB or IEC approval for the conduct of the study and the ICF must be provided to Bellerophon Pulse Technologies LLC or its designee.

10.1.2. Medical History

At Screening, relevant medical history and demographics (sex, race, and ethnicity) will be assessed. Medical history is to include the reason for hospital admission.

10.1.3. Prior and Concomitant Medications

All prior and concomitant medications, including all over-the-counter medications and all current COVID-19 treatments (all therapies prescribed for the treatment of COVID-19), will be recorded.

10.1.4. Physical Examination

A physical examination of the following body systems should be performed. Height and sex will be recorded during screening to calculate ideal body weight as used to program INOpulse dose. It is recommended the following body systems are reviewed:

- Head and neck
- Skin
- Eyes, Ears, Nose & Throat
- Respiratory
- Cardiovascular
- Musculoskeletal
- Abdomen
- Neurological
- Genitourinary
- Lymphatic
- Extremities
- Other

10.1.5. Chest Imaging

A chest CT scan or x-ray performed following the onset of symptoms and within 14 days prior to randomization. If clinically indicated per the Investigator, another chest CT scan or x-ray will be performed any time prior to discharge.

10.1.6. RT-PCR COVID-19 Test

Confirmation of viral infection will be performed using COVID-19 RT-PCR from an upper respiratory tract specimen within 4 day of randomization. If the initial COVID-19 RT-PCR swab is negative and there is still a high suspicion of COVID-19 infection, a repeat swab sample can be taken for RT-PCR testing. Another sample should be obtained from the nasopharynx or bilateral nares using a swab at End of Treatment (Up to Day 28).

10.1.7. Vital Sign Measurements

Vital sign measurements will include heart rate (HR), respiratory rate (RR), blood pressure (BP, systolic and diastolic), and temperature. Oxygen flow rate and any changes to flow rate will be documented. SpO₂ will also be documented and monitored to ensure levels remain >80% during the study and >89% upon initiation of treatment on Day 0.

10.1.8. Respiratory Failure Status

Respiratory failure is defined as one of:

- Endotracheal intubation and mechanical ventilation
- Extracorporeal membrane oxygenation
- High-flow nasal cannula oxygen delivery (i.e., reinforced nasal cannula delivering heated, humidified oxygen with fraction of delivered oxygen ≥ 0.5 and flow rates of ≥ 30 l/min)
- Noninvasive positive pressure ventilation
- Clinical diagnosis of respiratory failure with initiation of none of these measures only when clinical decision-making is driven solely by resource limitation or in the event the subject is not intubated due to do not intubate (DNI) or do not resuscitate (DNR) status

10.1.9. 12-Lead Electrocardiogram (ECG)

12-Lead ECGs will be obtained and read locally after the subject has rested in a supine position for at least 5 minutes. Date, time, heart rate, and ECG interpretation will be recorded.

10.1.10. 8-point NIAID Ordinal Scale

The ordinal scale is an assessment of the subject's clinical status. The subject's clinical status should be assessed as described in **Table 2** and documented in medical records. Assessments should be performed every morning when subjects are hospitalized and via phone if discharged from the hospital as detailed in **Table 2**.

The 8-point NIAID Ordinal Scale is provided on the following page.

The scale is as follows:

Score	Outcome
1	Death
2	Hospitalized, requiring mechanical ventilation or ECMO
3	Hospitalized, requiring non-invasive ventilation or high flow oxygen
4	Hospitalized, requiring supplemental oxygen
5	Hospitalized, not requiring supplemental oxygen - requiring ongoing medical care (COVID-19 related or otherwise)
6	Hospitalized, not requiring supplemental oxygen - not requiring ongoing medical care (COVID-19 related or otherwise)
7	Not hospitalized - limitation on activities and/or requiring home oxygen
8	Not hospitalized, no limitations on activities

10.1.11. Pregnancy Test

Females of childbearing potential must have a negative serum or urine pregnancy test as described in **Table 2**. All female subjects should take adequate precaution to avoid pregnancy by using two highly effective birth control methods for the duration of the study, which includes:

- Combined (estrogen and progestogen containing) hormonal contraception associated with inhibition of ovulation:
 - oral
 - intravaginal
 - transdermal
- progestogen-only hormonal contraception associated with inhibition of ovulation:
 - oral
 - injectable
 - implantable
- intrauterine device (IUD)
- intrauterine hormone-releasing system (IUS)
- bilateral tubal occlusion
- vasectomised partner
- sexual abstinence
- diaphragm
- condom with spermicide

Sexually active males at risk of causing a pregnancy must ensure their female partner(s) are using two methods of birth control (as described above) for the duration of the study.

10.1.12. Methemoglobin

Methemoglobin will be assessed prior to initiating INOpulse, during the 1st hour (every ½ hour) of the first dose of INOpulse and approximately 4-5 hours after initiating INOpulse therapy. Methemoglobin should be < 3% and SpO₂ >89% (with supplemental O₂ required) prior to continuing with treatment.

Following initiation of treatment, methemoglobin will be assessed twice daily while on INOpulse. Levels should not exceed >7%, otherwise the study drug should be interrupted and/or discontinued.

Sponsor will provide Masimo RAD-57 with rainbow probe to monitor methemoglobin in subjects treated with INOpulse.

Criteria for Study Drug Interruption: If methemoglobin exceeds 7%, SpO₂ falls below 80%, or clinically significant iNO-related adverse events are observed, INOpulse therapy should be interrupted. INOpulse therapy may be re-started at the discretion of the Investigator.

Criteria for Study Drug Discontinuation: If methemoglobin > 7% is sustained or severe respiratory failure, multi-organ failure and/or other conditions arise that impair the ability of the subject to receive INOpulse, INOpulse therapy should be permanently discontinued. Severe respiratory failure does not include subjects that require use of High Flow Nasal Cannula \leq 15L/minute (these subjects can continue to receive INOpulse treatment).

10.1.13. Laboratory Evaluation

The following blood tests will be performed locally: CBC with differential, chemistry panel (sodium, potassium, chloride, CO₂, BUN, creatinine, glucose), LFTs (AST/ALT and total bilirubin), troponin (High Sensitivity Cardiac Troponin [Hs-cTN]), D-Dimer, NT-pro-BNP (if NT-pro-BNP is not available locally, BNP can be drawn and converted using the online calculator: <https://www.cardio.med.tohoku.ac.jp/calc/nt-probnp.html>), LDH, fibrinogen, ferritin, triglycerides and pro-calcitonin.

If available at the local lab, also include CRP, Von Willebrands Factor, Factor VIII Activity, Protein C, Protein S, Homocysteine, Antithrombin 3, Thrombelastography (TEG), G6PD deficiency and Prothrombin gene G2021A.

Lab results obtained within the previous 48 hours of randomization are acceptable for screening purposes if there has not been a significant change in the subject's clinical status.

10.1.14. Symptomatic Rebound Testing Post INOpulse Discontinuation

Subjects receiving INOpulse should be monitored every 30 minutes for 1 hour after discontinuation of treatment, including early discontinuation subjects, for signs and symptoms of rebound (eg, systemic arterial oxygen desaturation, hypoxemia, bradycardia, tachycardia, systemic hypotension, shortness of breath, near-syncope, and syncope). If symptomatic rebound is observed, treatment with INOpulse should be re-started and the Investigator should contact Bellerophon.

10.1.15. Adverse Events

Adverse events, including serious AEs, will be assessed daily while hospitalized and at all study visits until End of Study. If an AE or SAE occurs while the subject is at home, then either the subject, the subject's caregiver or family member, or other responsible person will contact the study coordinator or Investigator at the research site and that person will record, assess, and report the event as indicated.

10.1.16. Drug Dispensing – Treatment Period

Prior to drug administration, the INOpulse® delivery device will be programmed and set up as per the INOpulse® Instructions for Use. Subjects will be instructed to notify the clinic staff if they hear an audible alert tone and/or if they notice flashing/steady amber or red lights from the INOpulse® delivery device during drug administration. Subjects will use the INOpulse for 24 hours daily until resolution of hypoxemia, protocol defined respiratory failure, hospital discharge or Day 28, whichever occurs first. In instances where continuous INOpulse dosing is not feasible (eg, due to PPE limitations), INOpulse should be used a minimum of 12 hours daily. Subjects may use 1 to 4 cartridges daily depending upon the duration of treatment (maximum of 28 days).

Safety will be assessed throughout the study by monitoring vital signs, methemoglobin, SpO₂ and adverse events.

All devices and cartridges will be returned to the Sponsor at the end of the study.

10.1.17. INOpulse Device Usage Download

Treatment usage will be automatically monitored by the INOpulse device. Following administration of the last dose of INOpulse, site research team personnel will download the usage data from the INOpulse device on the same day. In the event that the INOpulse device is returned to the Sponsor rather than the site, the usage data will be downloaded by the Sponsor or designee.

11. INOPULSE INVESTIGATIONAL STUDY DRUG AND DEVICE

Subjects will be treated by means of an INOpulse device using an INOpulse cannula.

11.1. Inhaled Nitric Oxide

The active study drug, nitric oxide for inhalation (iNO), will be provided in size 0.074 liter aluminum cartridge at a concentration of 6.0 mg/L (4880 ppm).

Matching placebo will be supplied in size 0.074 liter aluminum cartridge containing N2, 99.999% gas, identical to that of the active drug cartridge (iNO 125) to ensure double-blind is maintained.

The study subject's characteristics that are used by the INOpulse device to administer the study drug at the appropriate dosage, i.e., the subject's sex and height, will be assessed during screening and verified by research staff in order to confirm the INOpulse device is programmed correctly.

INOpulse cannot be used concurrently with PAP or PEEP.

INOpulse cartridges will be labelled for the PULSE-CVD19-001 program. All cartridges will meet the requirements for this clinical trial.

The investigational study drug, iNO, will be manufactured by Mallinckrodt Pharmaceuticals located in Part Allen, Louisiana USA.

11.2. INOpulse Device Description and Operation

The INOpulse Instruction for Use Guide provides complete guidance on the features of the INOpulse device.

11.3. Packaging and Labeling of Study Products

INOpulse study drug, device and cannula will be provided by Bellerophon Pulse Technologies LLC and clinical packaging and labeling will be done by a third party vendor in accordance with all legal and regulatory requirements of each country in which the study is being performed.

11.3.1. Storage

The study drug is to be stored in accordance with the storage/temperature requirements specified on the study drug labels. The INOpulse device should be stored within the recommended operating conditions specified in the INOpulse Instruction for Use, provided as a separate document.

In the hospital, the INOpulse study drug cartridges and devices should be stored in a secured, temperature controlled, and limited access area.

The Sponsor or their designee reserves the right to inspect the investigational product storage area at the Investigator site before and during the study. The INOpulse study drug and device will only be used solely for the purposes of this study.

11.3.2. Dispensing

Only subjects participating in the study may receive INOpulse study drug and device. Authorized, medically trained research team members will initially administer the INOpulse study drug and device to subjects.

The study subject's characteristics that are used by the INOpulse device to administer the study drug at the appropriate dosage, i.e., the subject's sex and height, should be checked and verified by research staff and entered into the IRT in order to confirm the INOpulse device is programmed correctly. The IRT will determine the treatment group and will be used to capture the parameters that should be set in the INOpulse device.

11.3.3. Accountability of Investigational Study Products

Investigational product accountability records for the investigational products mandated by the Sponsor in accordance with all applicable regulatory requirements must be kept current and should include, but not be limited to:

- the dates, quantities, and unique identification number of investigational products received from the Sponsor
- subject identification, date, amount, and unique identification numbers dispensed
- date, amount, and unique identification numbers of investigational products returned, as appropriate

Electronic systems may be utilized to assist in the capture and maintenance of this information. These records must be made available for inspection by the Sponsor or their designee during the course of the study.

The Investigator or designee is responsible for the accountability of all used and unused study supplies. The Investigator or designee will maintain accurate INOpulse study drug and device accountability records documenting date, quantities, and unique identification numbers of supplies received, dispensed, returned, and accounts of any INOpulse study drug and device lost, missing, or damaged. The Investigator or designee will retain copies of these logs on file.

At the conclusion of the study, a final inventory of study drug will be performed by the Sponsor or their designee. Any supplies which cannot be accounted for will be documented.

Any remaining INOpulse drug and devices at the end of the study will be handled as per Sponsor instructions (e.g., returned to Sponsor, CDC or their designee).

11.4. INOpulse Study Drug and Device Disposition

Used and unused INOpulse study drug cartridges and devices should not be destroyed or disposed of by the site, the distribution center, or by the subject. The used and unused INOpulse cartridges and devices will be returned regularly from the site to the CDC and/or manufacturing facility, utilizing a third party carrier.

Collection of used and unused INOpulse study drug cartridges and devices will be outlined in the study specific Distribution Plan.

12. RANDOMIZATION, BREAKING OF BLINDED CODES AND INTERACTIVE RESPONSE TECHNOLOGY (IRT) SYSTEM

12.1. Randomization and Blinding

Randomization will be performed using an IRT system. Randomization will occur ONLY after the subject has signed the informed consent, has been enrolled into the study, and has met all Inclusion and Exclusion criteria.

Blinded study drug should be started at the Baseline/Randomization visit.

All study drug cartridges will be labeled with informative language that each cartridge contains up to 6.0 mg/L (4880 ppm) NO gas to allow for compliance with compressed gas transportation regulations while maintaining a blinded label in the blinded treatment phase. All study labels will indicate the kit number and all drug cartridges will be labeled with a blinded unique identification number prior to shipment to the investigative site. Drug cartridges are intended for use by a single subject who will be assigned the corresponding kit number on the study label by the IRT. Similarly, all INOpulse devices will be uniquely identified, and tracked and controlled by the IRT.

12.2. Breaking of Blinded Codes

The blind may be broken only if specific urgent treatment would be dictated by knowing the treatment status of the subject.

The Investigator or designee will be able to call or login to the IRT to unblind a subject. It is **strongly recommended** to discuss the case with the Sponsor's medical monitor before unblinding.

The date, time, and reason for the unblinding must be documented in the CRF, and the Sponsor's medical monitor must be informed as soon as possible.

12.3. Interactive Response Technology (IRT)

Selected individuals at each study center will be authorized to have password protected access to the designated portions of the IRT system. Authorized individuals will interact with the IRT in accordance with the user manual. The IRT will be used by the site to assign subjects randomization numbers, dose cohorts, and INOpulse drug/device supplies.

13. ADVERSE EVENTS AND DEVICE DEFICIENCIES

At each study, the Investigator will determine whether any AE has occurred. The Investigator will also instruct the subject to contact the Investigator (or designee) in between study visits to report any AEs.

Adverse events will be coded according to the most current MedDRA classification.

The Investigator will record the nature, severity, treatment and outcome of the AE, and will determine their association to the investigational product or procedures involved in the study.

13.1. Definitions

13.1.1. Adverse Event

An AE is any untoward medical occurrence associated with the use of an investigational product in humans, whether or not considered investigational product related.

An AE can be any unfavorable or unintended sign (e.g., an abnormal laboratory finding), symptom, or disease temporally associated with the use of an investigational product, without any judgment about causality. This includes any events that occur during investigational product administration or, if present prior, have worsened in severity.

The Investigator will determine and record the seriousness, severity, relationship, and outcome for all AEs.

13.1.2. Adverse Device Effect

Adverse device effect (ADE) is an AE related to the use of an investigational medical device. This includes an AE resulting from insufficiencies or inadequacies in the instructions for use, the deployment, the implantation, the installation, the operation, or any malfunction of the investigational medical device.

13.1.3. Device Deficiency

Device deficiency is defined as an inadequacy of a medical device related to its identity, quality, durability, reliability, safety or performance, such as malfunction, misuse, or use error and inadequate labeling. All device deficiencies should be reported including outcome of device deficiency, regardless of whether they lead to an adverse event.

13.1.4. Suspected Adverse Reaction

A suspected adverse reaction (SAR) is an AE for which there is a reasonable possibility that the investigational product caused the AE. For the purposes of IND safety reporting, possibility means there is evidence to suggest a causal relationship between the investigational product and the AE. Suspected adverse reaction implies a lesser degree of certainty about causality than adverse reaction, which means any AE caused by an investigational product.

13.1.4.1. Unexpected Adverse Event or Unexpected Suspected Adverse Reaction

An AE or SAR is considered unexpected if it is not listed in the adverse reactions section of the Investigator Brochure, or is not listed at the specificity or severity that has been observed.

Unexpected, as used in this definition, also refers to AEs or SARs that are mentioned in the Investigator Brochure as occurring with a class of drugs, or as anticipated from the pharmacological properties of the drug, but are not specifically mentioned in the adverse reaction section as occurring with the particular drug under investigation.

13.1.5. Serious Adverse Event or Serious Adverse Reaction

A SAE or SAR is considered serious if, in the view of either the Investigator or Sponsor, it results in any of the following outcomes:

- Death
- A life-threatening AE
- Inpatient hospitalization or prolongation of existing hospitalization
- A persistent or significant incapacity or substantial disruption of the ability to conduct normal life functions, or
- A congenital anomaly/birth defect

Important medical events that may not result in death, be life-threatening, or require hospitalization may be considered serious when, based upon appropriate medical judgment, they may jeopardize the subject and may require medical or surgical intervention to prevent one of the outcomes listed in this definition. Examples of such medical events include allergic bronchospasm requiring intensive treatment in an emergency room or at home, blood dyscrasias or convulsions that do not result in inpatient hospitalization, or the development of drug dependency or drug abuse. A planned hospitalization for pre-existing condition, or a procedure required by the protocol, without a serious deterioration in health, is not considered to be a SAE.

If the subject develops respiratory failure, as defined in this protocol, it will be considered an SAE. This classification of serious events includes device deficiencies that might have led to a SAE if (a) suitable action had not been taken; or (b) intervention had not been made; or (c) circumstances had been less fortunate.

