2. SYNOPSIS

Name of Sponsor/Company: Bellerophon Pulse Technologies LLC
Name of Investigational Drug/Device Combination Product: Inhaled Nitric Oxide (iNO) / INOpulse
Title of Study: A RANDOMIZED, DOUBLE-BLIND, PLACEBO-CONTROLLED, STUDY TO ASSESS THE EFFICACY AND SAFETY OF PULSED, INHALED NITRIC OXIDE (iNO) VERSUS PLACEBO IN SUBJECTS WITH MILD OR MODERATE CORONAVIRUS DISEASE (COVID-19)
Study center(s): Multiple center study enrolling approximately 500 subjects.
Principal Investigator: TBD
Study period: First subject enrolled (planned): 2Q2020 Study completion: After the last subject completes 30 day follow up of the last iNOpulse dose
Duration of treatment: Subjects will receive placebo or iNO125 mcg/kg IBW/hr for 24 hours daily until resolution of hypoxemia, protocol defined respiratory failure, hospital discharge or Day 28, whichever occurs first. In instances where continuous INOpulse dosing is not feasible (eg, due to PPE limitations), INOpulse should be used a minimum of 12 hours daily.
Study Objectives: Primary Objective: The primary objective in this study is to verify the efficacy of iNOpulse in subjects with COVID-19. Secondary Objective: The secondary objective in this study is to evaluate the safety of iNOpulse in subjects with COVID-19.
Endpoints: Primary Endpoint: Proportion of subjects who died or had respiratory failure through Day 28. Respiratory failure is defined as one of: 
 • Endotracheal intubation and mechanical ventilation • Extracorporeal membrane oxygenation • High-flow nasal cannula oxygen delivery (i.e., reinforced nasal cannula delivering heated, humidified oxygen with fraction of delivered oxygen ≥ 0.5 and flow rates of ≥ 30 l/min) • Noninvasive positive pressure ventilation • Clinical diagnosis of respiratory failure with initiation of none of the above listed measures only when clinical decision-making is driven solely by resource limitation or in the event the subject is not intubated due to do not intubate (DNI) or do not resuscitate (DNR) status
Secondary Endpoints: 
 1. 8-point NIAID ordinal scale (Table 1) assessed at Days 7, 14, 28 and day of discharge 2. Proportion of subjects to recover, defined as return to room air or baseline oxygen requirements, or discharged alive from hospital [Through Day 28] 3. Proportion of subjects discharged alive from hospital [Through Day 28]

4. Duration of hospitalization [Through Day 28]
5. Mortality [Through Day 28]

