7. ENDPOINTS

7.1. Primary Endpoint

Proportion of subjects who died or had respiratory failure through Day 28.

Respiratory failure is defined as one of:

- Endotracheal intubation and mechanical ventilation
- Extracorporeal membrane oxygenation
- High-flow nasal cannula oxygen delivery (i.e., reinforced nasal cannula delivering heated, humidified oxygen with fraction of delivered oxygen ≥ 0.5 and flow rates of ≥ 30 l/min)
- Noninvasive positive pressure ventilation
- Clinical diagnosis of respiratory failure with initiation of none of these measures only when clinical decision-making is driven solely by resource limitation or in the event the subject is not intubated due to (DNI) or do not resuscitate (DNR) status

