7.3. Safety Endpoint

Proportion of subjects with adverse events leading to study drug discontinuation [Through Day 28]

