9. SUBJECT DISCONTINUATION, WITHDRAWAL AND TERMINATION FROM THE STUDY

9.1. Subject Discontinuation from Study Drug/Device

Vital status (whether alive or dead) will be determined on all subjects who prematurely discontinue. The specific reason for discontinuation will be documented. Subjects may be discontinued due to the following:

1. In the opinion of the Investigator, it is in the subject's best interests to discontinue study drug.
2. Subject no longer wishes to continue using the drug/device.
3. A subject becomes pregnant.
4. In the opinion of the Investigator, the subject experiences clinically significant rebound defined as clinically significant cardiopulmonary instability such as systemic arterial oxygen desaturation, hypoxemia, bradycardia, tachycardia, systemic hypotension, shortness of breath, near-syncope, and syncope occurring after acute withdrawal of study drug.
5. If methemoglobin $> 7\%$ is sustained or severe respiratory failure, multi-organ failure and/or other conditions arise that impair the ability of the subject to receive INOpulse, INOpulse therapy should be permanently discontinued.

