13.6 Safety Analyses

The primary safety endpoint is the proportion of subjects who experience adverse events (through Day 28) leading to study discontinuation. This proportion will be displayed overall for all subjects, and by treatment group

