13.6.2 Adverse Events

Treatment-Emergent Adverse Events (TEAEs) are defined as any AEs with an onset date on or after the date of the first dose of IP or any worsening of a preexisting medical condition/AE with onset after the start of IP and throughout the study. An AE leading to treatment discontinuation is defined as an AE where action taken on study drug is Drug Withdrawn. AEs will be coded using the Medical Dictionary for Regulatory Activities MedDRA version 23.0.

An overall summary of TEAEs, including the number of events reported, the number and percentage of participants reporting at least one TEAE, the number and percentage of participants discontinuing due to an adverse event, the number and percentage of participants with at least one serious adverse event, and the number and percentage of deaths will be presented.

The most frequent adverse events ($\geq 5\%$) will be compared between the INOpulse and placebo groups using a forest plot. The forest plot will display odds ratios of the incidence rate for each AE along with 95% confidence intervals.

A table of all anticipated and unanticipated deaths due to any cause, with number and frequency of such events in each arm/group of the clinical study, as well as the number of occurrences for each event. This also requires notification if the death is causally related to treatment for each reporting group.

A breakdown of the number and percentage of participants reporting each adverse event, categorized by System Organ Class (SOC) and preferred term (PT), will be presented. Note that counting will be by participant not event and participants are only counted once within each SOC and PT.

A further tabulation of these data, categorized by relationship to INOpulse, will be presented. Participants with multiple events within a particular body system or preferred term will be counted under the category of their drug-related event (related and not related) within SOC and PT. Relationship to INOpulse is categorized as related (rated "possible" or "related" in the CRF) or not related (rated "unlikely" or "not related" in the CRF).

A summary of events reported, categorized by severity, will also be provided. Participants with multiple events within a particular SOC and PT will be counted under the category of their most severe event in the following order: severe > moderate > mild within that SOC and PT.

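### On-treatment respiratory failures coded as drug withdrawal count in both the safety and the primary efficacy endpoint, so a benefit on iNO could offset an excess of other adverse-event withdrawals

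*Protocol*

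**What the plan says.** - **Primary endpoint** (Protocol 7.1): "Proportion of subjects who died or had respiratory failure through Day 28". Protocol 10.1.8 and SAP 10.0 define respiratory failure mainly by the support given, plus a clinical diagnosis where support is withheld because of resource limits or a DNI/DNR order.
- **Safety endpoint** (Protocol 7.3, repeated in SAP 9.0): "Proportion of subjects with adverse events leading to study drug discontinuation [Through Day 28]". It is the only endpoint listed for the secondary objective, which is safety.
- **How the SAP identifies it** (SAP 13.6.2): "An AE leading to treatment discontinuation is defined as an AE where action taken on study drug is Drug Withdrawn".
- **Respiratory failure as an adverse event** (Protocol 13.1.5): "If the subject develops respiratory failure, as defined in this protocol, it will be considered an SAE".
- **Respiratory failure and treatment** (Protocol 10.1.16): "Subjects will use the INOpulse for 24 hours daily until resolution of hypoxemia, protocol defined respiratory failure, hospital discharge or Day 28". Protocol 9.1 also lists, among the reasons for permanent discontinuation, "severe respiratory failure, multi-organ failure and/or other conditions arise that impair the ability of the subject to receive INOpulse".
- **Planned summary** (SAP 13.6): "The primary safety endpoint is the proportion of subjects who experience adverse events (through Day 28) leading to study discontinuation". The proportion is displayed overall and by arm. No interval and no test is specified.

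Neither document excludes primary-endpoint events from the safety endpoint. Neither says which action-taken code applies when drug stops for protocol-defined respiratory failure.

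**The concern.** Read together, these provisions let one event count twice: as an efficacy failure and as an adverse event leading to drug discontinuation. If iNO prevents respiratory failure, the placebo arm accumulates more of these events, and the safety proportion carries the efficacy effect inside it. An excess of withdrawals on iNO for other reasons, such as methemoglobin, nasal irritation, rebound or device problems, could be partly or wholly offset in the one figure named as the safety endpoint. Because the coding is unspecified, sites may also record the same clinical course differently, so the content of the endpoint could vary by site.

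**Working it through.** **Inputs from the documents.** SAP 8.1 and 13.5.3: death or respiratory failure (DRF) 15% on placebo and 6% on iNO, 500 subjects, 1:1. That gives 0.15 × 250 = 37.5, about 38 events, and 0.06 × 250 = 15 events. Deaths are included, so these are not counts of respiratory failure alone.

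**The plan's own figures.** The odds ratio (0.06/0.94)/(0.15/0.85) = 0.362 and its logarithm, −1.017, match SAP 13.5.3. Power from |log OR| × √(500 × 0.105 × 0.895 / 4) − 1.96 is 93.6%, close to the stated 93%; a pooled two-proportion formula gives 90.9%. The planning rates are therefore used as stated. The documents give no planning figure for the safety endpoint.

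**Assumptions not in the documents.**
- f: the share of DRF events that are on-treatment respiratory failures coded Drug Withdrawn. Range 0 to 1, taken as equal in both arms.
- Other adverse-event withdrawals: 5 of 250 (2.0%) on placebo and 18 of 250 (7.2%) on iNO, in different subjects from those with a counted DRF event.

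**Calculation 1: counts.** Placebo = 38f + 5; iNO = 15f + 18. P values are uncorrected chi-square on rounded counts.

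| f | Placebo /250 | iNO /250 | p | Reading |
|---|---|---|---|---|
| 1 | 43 (17.2%) | 33 (13.2%) | 0.21 | iNO looks safer |
| 0.75 | 33 (13.2%) | 29 (11.6%) | 0.59 | iNO looks slightly safer |
| 0.5 | 24 (9.6%) | 26 (10.4%) | 0.77 | signal gone |
| 0.25 | 14 (5.6%) | 22 (8.8%) | 0.17 | right direction, weakened |
| 0 | 5 (2.0%) | 18 (7.2%) | 0.006 | no masking |

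The arms are equal when 38f + 5 = 15f + 18, so f = 13/23, about 0.57. Only above that does iNO look safer.

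**Calculation 2: how large an excess could be cancelled.** Let the safety rate be fD + (1 − fD)t, where D is the DRF rate and t the other-withdrawal rate among the remaining subjects. Take t = 2% on placebo (assumed) and solve for the iNO t that equalises the arms. At f = 1 the placebo rate is 0.15 + 0.85 × 0.02 = 0.167, so iNO t = (0.167 − 0.06)/0.94 = 11.4%, an excess of 9.4 points. The excess is 6.9 points at f = 0.75, 4.5 at f = 0.5, 2.2 at f = 0.25 and zero at f = 0. With 5% on placebo and f = 1 it is 9.1 points.

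**Calculation 3: visibility.** With assumed t of 2% on placebo and 8% on iNO, a two-sided 5% comparison at 250 per arm would detect the iNO excess with about 87% power if no DRF event counted. That falls to 35% at f = 0.25, 7.5% at f = 0.5, 1.2% at f = 0.75 and 0.2% at f = 1. The plan specifies no such test; the figures only measure how far the signal is diluted.

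**The case against.** A reader might infer that every respiratory failure enters the safety endpoint, that the comparison mainly measures efficacy, and that an iNO excess of about 9 points would be hidden. The documents do not support that.

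- **Coding.** The treatment-duration text lists respiratory failure beside resolution of hypoxemia, discharge and Day 28 as a planned end of treatment. A site might reasonably not code that as Drug Withdrawn. Protocol 9.1 supports some overlap, but it refers to severe respiratory failure and does not settle the coding.
- **Timing.** The 15% and 6% include deaths and run to Day 28. Failures after study drug has stopped cannot withdraw it, and median treatment in the expanded access experience was 4 days (Protocol 5). So f = 1 is an upper bound.
- **Wording.** SAP 13.6 speaks of discontinuing the study. Subjects who fail are still followed, so on that literal wording the overlap would be small. But it conflicts with Protocol 7.3, SAP 9.0 and SAP 13.6.2.
- **Other outputs.** Nor can one infer that safety rests on a single proportion. Discontinuation events are tabulated by body system and preferred term (Table 14.3.2.4), all treatment-emergent events by relationship (Table 14.3.2.6), adverse events of special interest are defined, and the DMC sees unblinded data at least monthly.

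All four points stand and limit the size. They do not remove the overlap. The definition of respiratory failure rests on support given, so preferred terms need not map onto it, and no version of the endpoint free of primary-endpoint events is prespecified.

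**Conclusion.** The overlap follows from the documents' own definitions and applies to on-treatment respiratory failures recorded as Drug Withdrawn. Its size cannot be fixed, because f is not given. Under the assumed 5 vs 18 other withdrawals, the effect ranges from none at f = 0, through a lost signal at about one half, to a reversed direction above about 0.57. Those withdrawal counts, and an f equal in both arms, are assumptions. The problem is confined to the headline safety endpoint; it does not affect the primary efficacy analysis and does not make the other safety outputs uninformative. This is a cheap improvement rather than a flaw that undermines the trial.

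**What to change.** In SAP 13.6:
1. Keep the safety endpoint as defined and add a prespecified companion version that excludes events meeting protocol-defined respiratory failure. Give both by arm, with a difference and 95% CI, and interpret them together.
2. State how action taken is to be coded when study drug stops for protocol-defined respiratory failure, so that sites code alike.
3. Reconcile the SAP 13.6 wording on study discontinuation with the study drug wording in Protocol 7.3, SAP 9.0 and SAP 13.6.2.

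**Cost.** Respiratory failure status is already collected (Protocol Table 2), so no new data are needed, but adverse-event records must be linked to it because preferred terms will not identify these events reliably. The companion version also has limits. Subjects who fail early have less time to withdraw for other reasons, and this differs by arm if iNO works. Respiratory harm caused by the drug or device would drop out of it. It is therefore supportive and should not replace the defined endpoint.
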